## II. Specific Aims

Overview of Trial Design—The overall goal for these trials is to provide the data necessary for the design of definitive clinical trials. Specifically, we aim to test recruitment feasibility, the feasibility of POC electrolyte measurement and POC-directed management of the dialysis prescription, and to provide preliminary estimates of effect size with manipulation of UF rate, dialysate K, and dialysate HCO3. We will perform two related, randomized cross-over trials; Study A- dialysate interventions trial, consisting of 2 dialysate potassium interventions and 2 dialysate bicarbonate interventions (4 total cross-over interventions); and Study B-ultrafiltration rate intervention trial, consisting of 2 separate ultrafiltration rate strategies.

The central hypothesis underlying Study A and Study B is that the risk of clinically significant arrhythmias in HD patients can be reduced by altering components of the dialysis prescription.

**Aim 1—To test the feasibility and safety of POC-guided dialysate prescription adjustment and the feasibility of limiting UF rate in HD patients.** The current studies will pilot our educational strategies and the dialysate potassium, dialysate bicarbonate and UF intervention strategies to test their feasibility in a multi-center setting. They will test the hypothesis that  $\geq 80\%$  adherence with proposed interventions is feasible, and that the safety need for unscheduled dialysis or severe abnormalities in potassium and bicarbonate will be minimal.

**Aim 2—To assess recruitment feasibility and retention rate for trials combining ILR insertion to monitor arrhythmia and interventions using POC-guided dialysis prescription or UF rate manipulation.** Screen failures and retention rates will be captured and analyzed. Whether recruitment rates  $\geq 1$  patient per month and retention rate  $> 90\%$  are achievable in each study will be tested.

**Aim 3—To refine effect estimates of the change in monthly CSA duration during Study A (dialysate potassium intervention to maximize vs. minimize intradialytic potassium removal) and Study B (aggressive vs. conservative ultrafiltration rate).** Refining estimates of change in CSA with each pair of interventions will provide key information necessary for design of definitive trials. Whether CSA decreases with minimization of potassium removal, alkalosis limitation and UF rate minimization will be tested.

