## **V. Description of Study Procedures**

Two related, randomized cross-over trials will be performed; Study A-a dialysate interventions trial, consisting of 2 dialysate potassium interventions and 2 dialysate bicarbonate interventions (4 total cross-over interventions); and Study B- an ultrafiltration rate intervention trial, consisting of 2 separate ultrafiltration rate strategies. A total of 20 patients will be enrolled in each trial. An overview of the study design is illustrated in **Figure 5 below**.

**ILR Intervention**— Consent and ILR placement at the local site will be followed by a one-month baseline observation period. ILR placement will be followed by wound check visits at 1 week and 1-month post implant. Outpatient insertion of ILR by study cardiologists will occur within 4 weeks of enrollment. Reveal LINQ™ (Medtronic) implantable monitors will be utilized.

**Arrhythmia Detection**—Detection of clinically significant arrhythmias (CSA) will be achieved using implantable loop monitors (ILR) inserted at the start of each trial. ILR tracings will be batch analyzed by study cardiologists blinded to randomized treatment. Tracings from ILR-detected events meeting automated, validated detection criteria for bradycardia, asystole, AF, sustained or non-sustained ventricular tachycardia (VT) will be manually reviewed at least once every two weeks. Clinically significant arrhythmias will be defined on the basis of arrhythmias likely to lead to sudden cardiac arrest or serious morbidity and mortality and will include atrial fibrillation (AF), asystole lasting  $\geq 3$  seconds, bradycardia  $\leq 40$  beats per minute lasting  $\geq 6$  seconds, sustained VT  $\geq 130$  beats per minute lasting  $\geq 30$  seconds, and any sudden cardiac arrest. Positively adjudicated CSA will be entered into a study database and coded according to arrhythmia type, date and duration.

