**Description of Study Visits:**

Subjects will meet with a member of the study team for 8-11 study visits, during regular dialysis treatments at their outpatient clinics. Study activities for each of the study visits are described below. In addition to the study visits, subjects will continue their regularly scheduled dialysis treatments and must receive at least half of the treatments at their outpatient clinic (6 out of 12 scheduled) for each treatment period and the 30-day Baseline Observation Period. \*Procedures for missed treatments for each period are described below. Adverse events will be collected from the date of consent until study visit #11. For subjects who elect to keep the ILR LINQ device implanted at the end of the last treatment, adverse events and severe adverse events will be collected until a week after study visit #9.

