### **Study A Intervention - Dialysate K/HCO3 Trial: Monthly Visits:**

Study treatment to be started on the 1st Monday/Tuesday following the Week 4 Reveal Visit. There will be 4 crossover groups and subjects will rotate monthly through all the treatment groups in a random blinded order. Prior to initiation of all HD sessions, subjects will receive POC testing via the Abbott i-STAT, which requires approximately 100uL of blood. This testing, along with their treatment arm assignment, will drive the dialysate prescription for that specific HD session (see figures/tables further below). The 4 cross-over groups are listed below:

- i. Potassium Removal Maximization strategy, 1 month (low dialysate K)
- ii. Potassium Gradient-Minimization Strategy, 1 month (high dialysate K)
- iii. Acidosis Avoidance, 1 month (low dialysate bicarbonate)
- iv. Alkalosis Avoidance, 1 month (high dialysate bicarbonate)

There will be a 1-week washout period between subsequent interventions and during this week, participants' dialysate prescription will be determined by their dialysis physician. Dialysis treatment records will be reviewed at least monthly and standard of care labs will be recorded at visits 5 through 8.

Subjects enrolled in the optional substudy will press the button on the REVEAL patient assistant device to automatically trigger their implanted REVEAL LINQ ILR to record an EKG tracing each time their blood drawn is drawn by the dialysis staff prior to dialysis for POC testing. Subjects will also record a full transmission upon returning home from dialysis with the Carelink Transmitter.

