**Safety** will be assessed by calculating the incidence rate (complications per unit follow-up time) for serious adverse events and intervention-specific complications. Comparisons of incidence rate between interventions will utilize Poisson regression adjusted for randomization scheme and site. Exploratory analyses will assess age, sex, race, mean intra-dialytic weight gain, potassium concentration and HCO3 concentration in month prior to randomization on the incidence of adverse events. Given the pilot nature of the trials and major goal of informing feasibility estimates for definitive trials, P<0.05 will be considered significant in all safety analyses. No adjustments will be made for multiple comparisons given the pilot nature of the studies.

**Efficacy** estimates for Aim 3 will utilize the mean duration of CSA as the primary outcome. In the event of incomplete follow-up, this will be indexed to duration of follow-up time (e.g. minutes per day). Change in CSA duration between interventions will be analyzed using mixed effects linear regression with terms for treatment, research site, period, sequence, and random effects for subjects. Primary outcomes for the dialysate trial will compare CSA during potassium maximization vs. minimization, and acidosis vs. alkalosis avoidance. For the UF trial, aggressive vs. conservative UF will be compared. Physiologically, the washout period of 1-week in the dialysate trial and 1 weekend in the UF trial is sufficient to avoid the possibility of carryover effects. Potential for sequence effects is minimized by a design with uniform sequences (all treatments appear once within each sequence). Potential for carryover and randomization sequence effects will be analyzed by including terms for sequence and their interaction with treatment in the models.

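### Aim 1 claims that severe electrolyte events and unscheduled dialysis will be minimal, but the safety analysis plans no interval for any rate and no allowance for repeat events within patients

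*Combined protocol and SAP*

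**What the plan says.** Section II (Aim 1) sets out to test, among other things, that "the safety need for unscheduled dialysis or severe abnormalities in potassium and bicarbonate will be minimal". No number is attached to minimal there or elsewhere.

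Section VI, Safety Endpoints, defines the events. Study A counts laboratory excursions of potassium or bicarbonate, and unscheduled dialysis or hospitalization for them. Study B counts unscheduled dialysis or hospitalization for volume overload.

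Section VI, Statistics and Analysis, gives the method. Safety is assessed by "calculating the incidence rate (complications per unit follow-up time) for serious adverse events and intervention-specific complications". Then: "Comparisons of incidence rate between interventions will utilize Poisson regression adjusted for randomization scheme and site". The decision rule is that "P<0.05 will be considered significant in all safety analyses", followed by "No adjustments will be made for multiple comparisons given the pilot nature of the studies".

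Two contrasts within Section VI matter. Adherence is to be reported as a percentage with a 95% confidence interval, and recruitment and retention have numeric benchmarks, but safety rates have neither. The efficacy model includes random effects for subjects, whereas the safety model as described does not.

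On exposure, Section V says "A total of 20 patients will be enrolled in each trial". In Study A "subjects will rotate monthly through all the treatment groups in a random blinded order", and in Study B each subject has four weeks of each strategy.

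**The concern.** A claim that a rate is minimal needs an upper bound on that rate. The only inferential procedure given for safety asks a different question, namely whether two strategies differ. Where they do not differ, the result is silent about the level. Where events are uncommon, it is also likely to be non-significant when one strategy doubles the rate.

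The second weakness is the variance. Each patient contributes to every strategy, and in Study A a laboratory event can be counted at any of about 12 sessions per period. If such events cluster within a patient's month, ordinary Poisson standard errors are too small, and P values and any intervals built on them will be too narrow.

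At stake is the safety output that the pilot hands to the definitive trials: a bare rate and a P value would not tell their designers what level of harm has been excluded.

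**Working it through.** **Plan's own figure.** There is none to reproduce. The documents give no event rate, margin or power calculation for safety. Section IX (Frequency of Meetings) says that power to detect important safety signals will be adequate at the second DSMB analysis, but gives no figure.

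**Inputs.** 20 patients per trial (Section V) × 1 month per strategy = about 20 patient-months per strategy. With 12 scheduled sessions per period (Section V, Description of Study Visits), that is at most 20 × 12 = 240 sessions. Alpha is 0.05, taken as two-sided because the plan does not say. Event rates are assumptions, shown as a range.

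**Step 1: what the test can show.** Suppose each strategy has 20 events in 20 patient-months. The rate is 1.0 per patient-month on both, and the exact P value is 1. The two-sided 95% upper limit on each rate is nevertheless 1.54 per patient-month. The test is silent about this at any sample size.

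At the other end, with k events against 0 the exact two-sided P value is 2 × 0.5^k. Five against none gives 0.0625 and six against none gives 0.031.

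**Step 2: power for a true difference.** Independent Poisson counts with means 20λ and 20λ × ratio. Given the total, the split is binomial with probability 0.5 under the null. Exact conditional test, then likelihood-ratio test:

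| Lower rate λ (per patient-month) | Power, doubling: exact / LR | Doubling missed |
|---|---|---|
| 0.1 | 5% / 18% | 82–95% |
| 0.2 | 13% / 24% | 76–87% |
| 0.3 | 22% / 31% | 69–78% |
| 0.5 | 37% / 46% | 54–63% |
| 1 | 70% / 75% | 25–30% |
| 2 | 95% / 96% | 4–5% |

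A tripling from 0.1 is missed 64–83% of the time. Eighty per cent power for a doubling needs about 66 events in total, so λ = 66 / (20 × 3) = 1.1 per patient-month (1.25 by exact test, or 1.25 / 12 = about 10% of sessions).

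With only 10 completers, exact power for a doubling is 0.7% at 0.1 and 37% at 1 per patient-month.

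**Step 3: effect of clustering.** Let φ be the overdispersion of the counts (assumed). The standard error of the log rate ratio is √φ × √(1/(20λ) + 1/(40λ)) for a doubling.
- At λ = 1 and φ = 2 this is √2 × 0.274 = 0.387. Power with a correctly scaled test is Φ(0.693/0.387 − 1.96) = 43%.
- At λ = 2 and φ = 2 it is 72%.
- If φ = 2 is ignored, the nominal 5% test has size 2 × [1 − Φ(1.96/√2)] = about 17%.

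Simulation with assumed patient-by-period variation (SD of log rate 0.7 to 1) put the unadjusted test's type I error at about 12–40%. This range applies to frequent events: it runs from λ = 1 with log-SD 0.7 to λ = 3 with log-SD 1. A patient effect common to both periods largely cancels in the comparison, but still widens the interval for each strategy's own rate.

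**Step 4: what an interval would say.** Exact two-sided 95% upper limit with k events = χ²(0.975; 2(k+1)) / 2 / 20:
- k = 0: 0.184 per patient-month (× 12 = 2.2 per patient-year)
- k = 1: 0.279
- k = 3: 0.438

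**The case against.** Several points on the other side are sound.

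- **Rates are planned.** The safety paragraph starts with an incidence rate per unit of follow-up, so the P value is not the only safety output. Silence about intervals is also not a decision to omit them. This stands. The gap is the unstated interval and the variance method.
- **Non-significance as proof of safety.** A reader might infer that a non-significant result will be taken to show safety. No section says so. Section VI opens by calling all analyses exploratory and conservatively interpreted, and an unadjusted 0.05 threshold makes a harm easier to flag. No section makes a safety P value a go/no-go criterion for the definitive trials.
- **Most harms missed.** A reader might also infer that the test would miss most relevant harms. That depends on rates the documents do not give. Study A tests potassium and bicarbonate before every session, so frequent laboratory events are possible, and for these power can be adequate under independence.
- **Comparator.** In Study B one strategy is labelled standard of care, so that comparison does have an outside anchor. In each Study A pair both strategies are algorithm-driven, and the planned usual-care comparison concerns arrhythmia duration.
- **Other safeguards.** The DSMB reviews individual events and accumulated data, and severe abnormalities are handled off protocol. These protect participants but do not estimate the rates in Aim 1.
- **Ceiling.** Whether to fix a numeric ceiling for minimal is partly a matter of preference in a pilot of 20 patients.

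None of this supplies an interval, or a method that copes with repeat events.

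**Conclusion.** The point holds in a limited form. Aim 1 concerns an absolute rate, and a between-strategy test cannot address it; that needs no assumption about event rates.

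The power shortfall is conditional. It applies to events at about 0.3 per patient-month or less, where a doubling is missed about 70% of the time or more with 20 patient-months per strategy. At 1 to 2 per patient-month, power for a doubling is 70–96% if counts are independent, and lower if events cluster. If clustering is present and ignored, the test also rejects too often, by an amount that depends on assumed variation.

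The documents do not support the stronger readings that non-significance is planned as evidence of safety, or that most relevant harms would be missed whatever the rate.

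**What to change.** Revise the safety paragraph of Section VI as follows.

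1. For each strategy, report the event rate with a 95% confidence interval.
2. For each within-trial pair, report the rate ratio with a 95% confidence interval.
3. Use a method that allows for repeat events and within-patient correlation: Poisson regression with patient-clustered robust errors, or mixed-effects Poisson or negative binomial. Use exact limits when counts are very small. Because exact Poisson limits assume independent events, also give the number of patients with at least one event.
4. Base the Aim 1 safety statement on the upper limits, noting that zero events in 20 patient-months leaves a two-sided 95% upper limit of 0.18 per patient-month.
5. State that a non-significant comparison is not evidence of safety.

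Any numeric ceiling for minimal is for the investigators to choose. If they want one, it should be fixed before unblinding and with the 0.18 limit in mind.

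The cost is a change of wording and a slightly more complex model, with no new data. The drawback is that the safety conclusion for rare events will probably be inconclusive.

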After ILR placement, subjects will crossover between two UF rate interventions: 1) UF rate-restricted dialysis, in which UF rates are limited to a maximum of 10 mL/kg/hr for the duration of the session 2) UF rate-unrestricted dialysis. It is anticipated that patients with large interdialytic weight gains in the UF rate-restricted intervention may not achieve their target post-dialysis weight during the prescribed treatment time. In order to prevent progressive volume overload and the need for additional HD sessions to manage volume gains in this scenario, subjects will crossover weekly between the restricted

and unrestricted UF interventions. This weekly crossover accomplishes two important goals: First, it reduces safety concerns by ensure that any volume gained due to limiting the UF are constrained to one week and promptly addressed with unlimited UF the following week. Second, it increases separation between UF rates in the two interventions, since a higher UF-rate will be needed to address any weight and volume gains resulting from UF-rate restriction.

Investigators will be blinded. Subjects will not be blinded as it is not feasible to blind them to the goal UF and post-dialysis weight (typically self-measured); HD staff will have access to the algorithm in order to adjust UF rate accordingly. Following a one-month baseline observation period with usual care, subjects will undergo 4 weeks of each UF intervention administered in alternating weeks as described above, for a total study duration of 12 weeks. Data will be aggregated and results compared using a full month of data for each intervention.

**End of Study Procedures**—In order to maximize recruitment efficiency and the significant investment in undergoing ILR implantation, patients completing one study will be given the option of continuing to eligibility screening and enrollment for the alternate study. If subjects consent to both Study A and Study B, then the baseline observation period for the second study may be less than 1 month. Those refusing or ineligible will be offered ILR explanation.

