**\*Procedures for Missing Consecutive Dialysis Treatments During Intervention Periods in Study A:**

Subjects who have missed less than 6 consecutive weeks, can also "make-up" treatments with a 2-week extension that will begin on the first Monday or Tuesday upon their return to the dialysis clinic. Subjects will receive their last assigned intervention during these make up treatments and the study schedule and dates of their remaining study visits will be adjusted accordingly.

In the event that a subject does not receive outpatient dialysis at his or her usual outpatient dialysis clinic for six consecutive weeks or more, the subject will be reassessed by the site investigator for suitability before continuing in the trial. If deemed appropriate to continue in the study, the rules as described above will be applied so that the subject receives at least 6 dialysis treatments of the assigned intervention.

Although all intervention periods will be scheduled to start on the 1st Monday or 1st Tuesday of a week, no special provision will be made to extend the intervention period if subjects miss their treatment on these days, provided they are able to complete at least 6 dialysis treatments of the assigned intervention. The intervention will simply start on the next scheduled dialysis treatment.

**Study B Intervention- Ultrafiltration Rate Trial: Biweekly Visits:** Study treatment to be started on the Monday/Tuesday following the Week 4 Reveal Visit. There will be 2 treatments and subjects will rotate back and forth weekly during an 8-week period in a random order. Dialysis unit records will be reviewed at least monthly and standard of care labs will be recorded at visits 5 and 8.

- i. **Restricted UFR;** UFR  $\leq$ 10 ml/kg/hr: 4 alternating weeks
- ii. **Standard of Care/ Unrestricted UFR;** UFR as needed: 4 alternating weeks

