Study procedures ensure testing of electrolytes at each session (3x/week) in contrast to a frequency of as little as 1x/month in routine practice. Severe electrolyte abnormalities will thus be recognized earlier with study patients than in routine practice. Similarly, POC testing will ensure that the dialysis prescription will be adjusted according to the ambient potassium or bicarbonate at that dialysis session. In routine practice, follow-up testing at outpatient dialysis units typically has a turn-around time of hours (stat testing) or days (routine lab draws) which makes appropriate adjustment of the dialysis prescription unfeasible. Thus, study procedures may actually lower the risk of severe electrolyte abnormalities or risk of complications from those abnormalities. However, significant inaccuracy in the point of care testing results could modify the associated risks.

To further mitigate risk, patients with severe abnormalities in potassium ( $K>6.5$  or  $<3.0$ ) or bicarbonate ( $<20$  or  $>32$ ) will temporarily come off therapy and be treated off-protocol at the discretion of their clinician.

**Study B UF algorithms** are designed to either limit UF rates to  $\leq 10$  mL/kg/hour or to allow UF rates  $\geq 13$  mL/kg/hour. As discussed in the research summary, there is significant equipoise regarding the risk/benefit ratio of either strategy, as the use of high UF rates minimizes the risk of volume overload at the expense of rapid fluid shifts, whereas limiting UF rate minimizes the risk of rapid fluid shifts at the expense of increasing the risk of volume overload. Both strategies are routinely employed in clinical care. Thus, it is again unclear whether research-related risks are materially different than those in routine practice. As described in the Research Plan, subjects will cross over weekly between the unlimited and restricted UF treatments, thereby allowing removal of excess fluid accumulated during the restrictive week during the subsequent, unlimited week. This will limit any excessive fluid gains to a maximum of a few liters over the course of the restricted UF week thereby limiting the possibility of volume-related complications in the event patients fail to self-regulate intake of salt and water. Safety, will be further ensured because patients who show signs of significant volume overload will have the

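### Study B: the plan says one weekend rules out carryover, but its weekly alternation relies on fluid carried into the next week, and the planned sequence terms are not a usable check

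*Combined protocol and SAP*

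**What the plan says.** - **Carryover.** Section VI, Statistics and Analysis (Efficacy), asserts on physiological grounds that "1 weekend in the UF trial is sufficient to avoid the possibility of carryover effects".
- **Check.** The same paragraph assesses carryover and sequence effects by "including terms for sequence and their interaction with treatment in the models". The main model is a "mixed effects linear regression with terms for treatment, research site, period, sequence, and random effects for subjects". It does not say how period is coded for Study B.
- **Fluid.** Section V, on the weekly crossover, counts added separation of UF rates as a design goal, "since a higher UF-rate will be needed to address any weight and volume gains resulting from UF-rate restriction". Section VII (Study B UF algorithms) relies on the same mechanism for safety, "thereby allowing removal of excess fluid accumulated during the restrictive week during the subsequent, unlimited week".
- **Schedule.** Section V alternates the two interventions every week for eight weeks (weeks 5 to 12), with no usual-care week between them.
- **Contrast.** Section V says: "Data will be aggregated and results compared using a full month of data for each intervention". Section VI says: "For the UF trial, aggressive vs. conservative UF will be compared". The Study B Intervention paragraph in Section V labels the comparator "Standard of Care/ Unrestricted UFR". Secondary Analysis in Section VI also plans to compare each intervention with the usual-care period.

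**The concern.** The weekend cannot remove the fluid left by a restricted week. Section I describes it as free of dialysis, and Sections V and VII assign the removal to the following treatment week. Carry-forward of fluid and UF rate is therefore part of the design, while Section VI excludes carryover as a possibility.

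Aim 3 is meant to supply effect sizes for definitive trials. If the unrestricted weeks are mostly catch-up weeks, the Study B estimate may differ from the effect of restriction against usual care. A null result on the planned terms could then be read as support for the no-carryover statement when those terms carry almost no information about it.

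**Working it through.** The carryover statement has no figure attached, so there is none to reproduce. The check is of the design itself.

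**Inputs.** Eight alternating weeks, four of each intervention (Section V). Twenty subjects (Section V), with 10 per sequence assumed. Full adherence assumed. R is a restricted week and U an unrestricted week. Let c be the extra CSA duration in a week because the preceding study week was restricted. Week 5 has no preceding study week, so it carries none.

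| Sequence | Weeks 5 to 12 | U weeks after R | R weeks after R |
|---|---|---|---|
| Restricted first | R U R U R U R U | 4 of 4 | 0 of 4 |
| Unrestricted first | U R U R U R U R | 3 of 4 | 0 of 4 |

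**1. Exposure.** Unrestricted weeks after restriction: 10 × 4 + 10 × 3 = 70 of 80 (87.5%). Restricted weeks after restriction: 0 of 80.

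**2. Where an omitted carryover goes.**
- Treatment contrast (restricted minus unrestricted): -c in the restricted-first sequence and -0.75c in the other. The average is (-1 - 0.75)c/2 = -0.875c per week, or 4 × -0.875c = -3.5c on a four-week total.
- Sequence means: 4c/8 = 0.5c and 3c/8 = 0.375c. The difference is 0.125c, and it is a between-subject comparison.

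**3. What sequence-by-treatment measures.** Within each sequence, treatment is fixed by whether the week is odd or even. The product of sequence and treatment is therefore an odd/even-week pattern. Rank of the fixed-effect matrix (intercept, sequence, period, treatment) before and after adding the interaction; site is left out and does not alter the aliasing:

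| Period coding | Before | After | df gained |
|---|---|---|---|
| Factor, 8 weeks | 10 | 10 | 0 |
| Aggregated, two periods | 4 | 4 | 0 |
| Linear trend | 4 | 5 | 1 |
| Two-week cycle | 6 | 7 | 1 |

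In the last two codings, the interaction coefficient is, in size, twice any even-minus-odd week difference. It takes up 0.175c (linear) or 0.25c (cycle) of carryover, and only because week 5 has no predecessor. The -0.875c and 0.125c split is the same in all three weekly codings.

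**4. An explicit carryover term.** In weeks 6 to 12 the previous treatment is always the opposite of the current one, so only week 5 separates the two. With weekly data, subject effects and period as a factor, adding a first-order carryover term raises the rank from 28 to 29, so it is estimable. The treatment variance rises from 0.025 to 0.229 residual variances: 0.2292/0.025 = 9.17-fold, or √9.17 = 3.03-fold in standard error. In aggregated data the term adds nothing (rank stays 4).

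**5. UF rate, for illustration only.** Suppose every session needs 13 mL/kg/hr (the Study B entry threshold) and restricted weeks are capped at 10. The shortfall is 3 per session. If it is fully removed in the next week, that week averages 13 + 3 = 16. Separation is then 16 - 10 = 6 instead of 13 - 10 = 3, so half of it comes from catch-up. Full catch-up is an assumption; the documents do not say how complete it is.

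**The case against.** The strongest reply is that the contrast is intended and disclosed. Section V sets out the alternation, explains the catch-up and counts it as a benefit, and Section VI calls the comparison aggressive versus conservative. On that view the higher UF rate after restriction is part of the treatment and not a bias. This largely stands. The plan does not define the primary Study B estimand as restriction versus usual care, and only the limit on interpretation is left unstated.

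It is also fair to say that all analyses are exploratory, that no decision rule depends on the sequence terms, and that a usual-care comparison is already planned. These points limit the consequence. They do not repair a statement that conflicts with the design, or a check that cannot do its job.

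A reader might go further and infer one of the following, which the documents do not support:
- **That arrhythmia carries over, or that the Study B estimate is biased by a known amount.** The documents establish carry-forward of fluid and UF rate. They give nothing on whether this changes CSA, so c may be zero, and no figure in minutes can be justified.
- **That carryover cannot be estimated at all.** It can in weekly data, but too imprecisely to be useful.
- **That Study A has the same defect.** Study A has a one-week usual-care washout and four treatments, and this working does not cover it.

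**Conclusion.** The point holds for Study B. The weekend statement in Section VI conflicts with Sections V and VII, and the passages must be reconciled. That conclusion, and the aliasing of sequence-by-treatment with period, do not depend on c. The sequence term is estimable, but it receives one seventh as much of any carryover as the treatment contrast does (0.125 against 0.875).

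The 70-of-80 count rests on full adherence and equal sequence sizes. Missed sessions or unequal allocation would change it. The fractions 0.875 and 0.125 assume carryover lasting one week only. The practical effect is confined to how the Aim 3 estimate for Study B may be read and used in planning; the adherence, safety and recruitment aims are untouched. It should be corrected, but it does not invalidate the pilot.

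**What to change.** For Study B only:

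1. Remove the statement that a weekend avoids carryover, and reconcile that paragraph with Sections V and VII. Do not use sequence or sequence-by-treatment as the carryover check. State how period is coded.
2. State that the Aim 3 estimate compares restricted with unrestricted weeks inside a weekly alternating regimen, catch-up fluid removal included. Add that it does not estimate restriction versus usual care, despite the comparator's label in Section V, and that carryover cannot be usefully separated from treatment.
3. Report mean delivered UF rate by arm and in the baseline month, with week 5 shown separately, so that readers can see how much catch-up occurred. Place the usual-care comparison already planned under Secondary Analysis beside the main estimate. Label it non-randomised and confounded with time, because the baseline month comes before both interventions.

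The cost is wording, one descriptive table from dialysis records already under review, and the placement of an analysis already planned. The treatment schedule does not change. The downside is a narrower interpretation of the effect estimate.
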